4.2 Intervention

Participants in the QL + AR condition will download and use a smoking cue extinction app that includes the features outlined in Table 1.

Table 1. AR App Features

FEATURE	DESCRIPTION	RATIONALE
Situation Menu	Participants will choose what situations/times of day are most appropriate for their AR sessions, although the app will provide general recommendations.	Tailoring treatment content to the individual and supporting choice; ¹ supporting autonomy. ²
Tutorials	Video tutorial on correct app use (e.g., placing AR stimuli), with unlimited interactive practice sessions.	Supporting competence; identified as a needed feature in preliminary work by the investigative team.
Rationale for Cue Exposure	Rationale for cue exposure to help quit smoking/support participant goals (video).	Supporting autonomy; ² providing purpose of the app and improving knowledge of benefits. ¹
Best Practices for AR Sessions	Specific guidelines for using the app (e.g., no smoking during sessions; no use of nicotine products before sessions, patch use ok).	“Expert advice” is an ideal feature for quit smoking apps. ³
Reminder Notifications	Participants will select frequency of reminder notifications to complete AR sessions.	Supporting autonomy; ² participants prefer to choose timing of reminders. ³
Progress Tracker	Participants will be able to view 1) their progress through the program overall, 2) changes in urge ratings over time, 3) daily cigarette use, and 4) use of NRT.	Supporting competence; ² consistent with mHealth frameworks; ¹ preferred feature in quit smoking apps. ^{3,4}

Troubleshooting	Available any time to support use of the app.	Quick access for app support.
Rewards	Linked app engagement and progress towards quitting (e.g., visual presentation of money saved by not smoking).	Rewards for quitting smoking commonly requested feature. ³
App Coach	Link to live App coaching by phone call.	Offers additional explanation of extinction goals as well as technical assistance for app.

¹Floryan et al., 2016; ²Ryan & Deci, 2000; ³Hartzler et al., 2016; ⁴McClure et al., 2016

App Use

Initial use of the app will occur in stages: Assess, Setup, Recommendations for Use, and Extras. Once users complete the stages, they will be able to use the app as needed on a daily basis. We describe all aspects of the app below, including those only relevant to Aim 2.

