Assess. Each morning, participants will be prompted to complete a daily diary to assess the following from the previous day: number of cigarettes smoked, NRT use, and tobacco craving. Because ongoing smoking during cue-exposure sessions will be counter-productive to extinction of urges, participants will need to self-report 48 hours of abstinence to advance to Setup. Achieving such short-term abstinence with quitline support/NRT should be feasible for at least 70% of participants (Shiffman et al., 1996; Shiffman et al., 2007).

Setup. Once the abstinence requirement is met, participants will personalize the app, learn the purpose of the app, and practice using AR. First, they will watch a video tutorial explaining the use of cue exposure. They will select their most relevant AR cues and situations in which they most commonly smoke and/or experience high cravings (e.g., upon waking, after meals, when stressed, with alcohol, with coffee, celebrating). They will receive a list of “best practices” for completing AR sessions (e.g., no smoking during sessions). Participants will next receive instruction on using the app for cue-exposure sessions, comprising a short video describing how to place the AR objects, followed by an interactive tutorial with real-time practice.

Recommendations for Use. Recommendations for daily use will be proactively provided, but also available for later review on demand. The app will recommend that participants complete 2-5 AR sessions per day. It will emphasize that the more often they use the app when experiencing craving, the more successful they will likely be in maintaining abstinence.

Extras. Participants will be introduced to all other features of the app: setting up reminder notifications, accessing the progress tracker, access to the App coach, and viewing of rewards.

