The Florida Tobacco Quitline is operated by RVO Health, the largest provider of tobacco cessation quitlines in the U.S. RVO Health's Quit For Life® program is an evidence-based tobacco cessation treatment delivered over phone, web, and text, and is grounded in social cognitive theory and the U.S. Public Health Service clinical guidelines (PHS Guideline, 2008). Quitline coaches use cognitive behavioral therapy, reinforcement, and principles of self-efficacy to promote effective behavior change. The quitline approach includes 5 key elements: setting a quit date, coping with triggers, effectively using medications, tobacco proofing, and social support. Phone counseling for cessation has been evaluated in randomized trials and effectiveness studies (Hollis et al., 2007; Orleans et al., 1991; Stead et al., 2013; Zhu et al., 2002). Individuals who enroll in the quitline's multi-call program receive three phone calls. They are mailed two weeks of NRT after the first phone call, to begin using on their quit date (coinciding with the second call). Participants will be provided with information about the study during their first phone call, and study staff will reach out to enroll participants in the study after receiving their contact information from the Quitline.

Study Arms

Quitline Only (QLO). Participants randomized to the QLO condition will receive an app that administers the daily diary questions for 5 weeks and shows their app and abstinence related progress. They will not receive any treatment via the app. Thus, they will receive usual care via the quitline and complete minimal daily assessments.

Quitline plus AR (QL+AR). Participants randomized to QL+AR will receive the AR app described in Aim 1. Initially, the app will only administer the daily diary questions. Once 48 hours of self-reported tobacco abstinence is achieved, the AR elements of the app will become available (see 4.2). Daily diary questions will continue for 5 weeks. AR extinction trials will occur daily until (1) the participant reports 3 consecutive days of smoking, in which case the AR trials will be suspended until another smoke-free 48 hours are reported, or (2) a

total of 5 weeks have elapsed since the start of app use.

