Aim 2a. The primary test of the efficacy of QL+AR over QLO will use logistic regression on biochemically-confirmed abstinence around 6 months after baseline survey completion. This will be performed on the 20 imputed data sets using those participants who exhibited 48 hours of abstinence (n=1450). The model will include demographics and smoking-related variables that were found to uniquely predict self-reported abstinence at 6 months based on preliminary analyses. A parallel analysis will be performed to evaluate efficacy for all enrolled (N=2072; i.e., beyond those who exhibit the required 48-hour abstinence to engage the AR intervention). A second test of effectiveness will use generalized estimating equations (GEE) with both the 5-week and 6-month abstinence as the outcomes. This approach permits evaluation of a change in abstinence from around 5 weeks to 6 months and an assessment of the intervention at around 5 weeks in the context of the primary outcome (using a timespecific contrast).

Aim 2b. Prospective moderators of the QL+AR intervention will be explored, separately, by extending the analyses described above through the inclusion of the moderator and the moderator x intervention as predictors of the dependent measure. A significant interaction term supports the variable as a moderator, which will be explored by assessing condition differences for each level of categorical moderators and for levels of continuous moderators created via median splits, tertiles, or quartiles. The following baseline measures will be evaluated: sex, nicotine dependence, trait cue reactivity, smoking status during treatment, quitline use, and NRT use.

Prospective predictors of the AR intervention will be evaluated using only participants from the QL+AR arm. Similar to the analyses described above, AR-related variables will be added to a logistic regression model of abstinence at around 6 months that includes demographics and baseline smoking-related variables found to be predictors of abstinence among QL+AR participants. The following variables will be explored: initial cue reactivity, extinction magnitude and latency, indices of treatment engagement, and App coach use.

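### As written, the two apps differ before 48 hours of abstinence: QLO has a progress display and QL+AR has diary questions only, in the period that decides entry to the primary analysis set

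*Combined protocol and SAP*

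**What the plan says.** Section 4.3 (Study Arms) describes the QLO app as one that "administers the daily diary questions for 5 weeks and shows their app and abstinence related progress". It adds that QLO participants get no treatment through the app. No abstinence condition or start day is attached to the display.

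For QL+AR the same section says: "Initially, the app will only administer the daily diary questions". It continues: "Once 48 hours of self-reported tobacco abstinence is achieved, the AR elements of the app will become available".

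Section 4.2 (App Use) sets out the QL+AR stages in order: Assess, Setup, Recommendations for Use, Extras. In Assess, "participants will need to self-report 48 hours of abstinence to advance to Setup". The remaining features come in Extras, the last stage: "setting up reminder notifications, accessing the progress tracker, access to the App coach, and viewing of rewards". Table 1 in section 4.2 lists the Progress Tracker as an AR app feature that supports competence. It shows users "their progress through the program overall, 2) changes in urge ratings over time, 3) daily cigarette use, and 4) use of NRT".

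Section 4.3 also describes on-demand App coaching, reached from within the app at any time during set daily hours. That paragraph states no abstinence condition.

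Section 5 (Aim 2a) runs the primary logistic regression "using those participants who exhibited 48 hours of abstinence (n=1450"). The analysis of all 2072 is described as parallel. The power calculation takes 725 of 1036 as reaching 48 hours in each arm.

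**The concern.** Selecting the primary set on an event after randomisation is easiest to defend when both arms have had the same experience up to that event. Here the AR content is withheld until 48 hours, so matching apps before that point look achievable. As written, they do not match: QLO has a progress display and QL+AR does not.

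If the display changes who reaches 48 hours, the two arms' primary sets contain different mixtures of participants. Suppose it brings some QLO participants through who then relapse. They enter the QLO denominator, have no counterparts in QL+AR, and lower the QLO 6-month rate, so QL+AR looks better without any AR effect. If the display discourages some participants, the shift goes the other way. Table 1 treats progress tracking as supportive, so an effect cannot be excluded, but no figure in the documents measures one.

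**Working it through.** **1. The text side by side**

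| | QLO | QL+AR |
|---|---|---|
| Before 48 hours reported | Diary, plus progress display (no condition stated) | Diary only |
| After 48 hours reported | Diary, plus progress display | Diary, AR sessions, tracker and other Extras |
| App coach before 48 hours | Not offered | Unclear: introduced in Extras (4.2), but no condition stated in the coaching paragraph (4.3) |

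Two separate statements put the QL+AR tracker after the threshold: the restriction to diary questions in 4.3, and the stage order in 4.2.

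**2. The plan's own figures**

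- Share reaching 48 hours: 0.70 × 1036 = 725.2 per arm, matching 725.
- Power for 10% v 15%, two-sided .05, with 5% of variance explained by other variables: effective n = 725 × 0.95 = 688.75 per arm. The pooled two-proportion formula gives 0.802, against the stated ≥ .80.
- Odds ratio: (0.15/0.85)/(0.10/0.90) = 1.588, against the stated 1.59.
- All randomised, QLO: 7% × 1036 = 72.5 abstinent. The 48-hour set: 10% × 725 = 72.5. The planning figures therefore imply almost no 6-month abstinence among those who never reach 48 hours.

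These figures reproduce. No stated number is wrong because of this point.

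**3. Illustration of unequal passage with no treatment effect**

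Assumptions, not in the documents:

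- QL+AR reaches 48 hours at 70%, with 10% of those abstinent at 6 months.
- QLO reaches 48 hours at proportion g.
- The participants who make up the difference have 6-month abstinence r.

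Formulas:

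- QLO rate in the 48-hour set: p = [0.07 + (g − 0.70) × r] / g, with n = 1036 × g.
- OR (QL+AR v QLO) = (0.10/0.90) / [p/(1 − p)].
- Two-sided rejection = Φ[(D − 1.96·s0)/s1] + Φ[(−D − 1.96·s0)/s1], where D = 0.10 − p, and s0 and s1 are the pooled and unpooled standard errors.

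Worked case, g = 0.75, r = 0: p = 0.07/0.75 = 9.33% (72.5 of 777). OR = 0.1111/0.1029 = 1.08. With D = 0.0067, s0 = 0.0152 and s1 = 0.0153, rejection is 0.072.

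| g (QLO) | r | QLO rate | OR | Two-sided rejection |
|---|---|---|---|---|
| 0.65 | 0 | 10.8% | 0.92 | 7.6% |
| 0.70 | any | 10.0% | 1.00 | 5.0% |
| 0.75 | 0 | 9.3% | 1.08 | 7.2% |
| 0.75 | 5% | 9.7% | 1.04 | 5.5% |
| 0.75 | 8% | 9.9% | 1.015 | 5.1% |
| 0.75 | 10% | 10.0% | 1.00 | 5.0% |

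The shift needs both an unequal share reaching 48 hours and an abstinence rate in the extra participants that differs from 10%.

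**The case against.** The asymmetry is read from summary sentences. The QLO display has no stated start day, so a reader who infers that it runs from the first day of app use goes beyond the text. What the text supports is that no abstinence condition is attached to it. In QL+AR, the 48-hour condition is said to open the AR elements, and a tracker is not one. Being introduced to a feature in Extras is also not an express lock. These points leave room for loose drafting, but the diary-only sentence and the stage order both point the same way. If the built apps already match, correcting the text is enough.

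The documents do not say that the QLO display is the Table 1 tracker, and someone who has not yet reached 48 smoke-free hours has little abstinence progress to see. Nothing shows that such a display moves several percent of an arm past the threshold. This stands, and is why the size remains unknown.

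A reader might also infer a specific inflation in favour of QL+AR. Eight extra points of QLO participants, none abstinent at 6 months, would give about 10.5% rejection. Both inputs would be invented; with 5% of those extra participants abstinent it is 6.3%, and the direction can reverse. The documents support neither a figure nor a sign.

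Finally, the parallel analysis of all 2072, with stated power above .80, does not select on the threshold. That is a real safeguard for the trial's overall conclusion, but it does not protect the test the plan names as primary.

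**Conclusion.** The point holds as an avoidable difference between arms in the period that fixes membership of the primary set. It rests on the literal wording of sections 4.2 and 4.3. The size and direction of any resulting bias are unknown. The illustrative values (OR about 1.08 or 0.92, two-sided error about 7%) assume a 5-point difference in the share reaching 48 hours, no treatment effect, and no 6-month abstinence among the participants who make up the difference. They shrink to nil as that abstinence rate approaches 10%.

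A reader might conclude that matching the display would make reaching 48 hours equivalent to a pre-treatment event. The documents do not support that. Only QL+AR participants unlock AR content at 48 hours, which could itself affect who reports abstinence, and App coach access before that point is not settled. The 48-hour set would still be selected after randomisation.

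**What to change.** - Reconcile section 4.2 (Table 1 and App Use) with section 4.3 (Study Arms and the App coaching paragraph), so that both arms' apps have the same non-AR content, including the progress display, until 48 hours of abstinence is reported. Which way to align them is the sponsor's choice.
- State whether the App coach can be reached before that point.
- Report the number and share reaching 48 hours by arm. The daily diary already collects what is needed.
- Present the 48-hour result beside the analysis of all 2072, which this selection does not affect.

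The cost is an app configuration change, if the built apps differ, and short text edits. Participants already run under a differing configuration must be flagged. No extra participants or data are needed, and the stated sample size and power are unchanged.

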4.4 Measures

AIM 1 Measures

Baseline Measures. Participants will complete a series of baseline measures, administered via REDCap link, to assess demographics, experience with AR, and smoking history.

Daily Diary Questions. Each morning, participants will report via the app: number of cigarettes smoked from previous day; previous day's use of NRT, e-cigarettes, and other tobacco products; and current urge to smoke, assessed on a 10-point Likert scale (see appendices).

Urge and Situation during AR Sessions. Participants will rate their urge (craving) to smoke on a single 10-point Likert scale. Single-item scales reduce participant burden when multiple ratings are required, and they have been found to be reliable and valid in assessing urge to smoke (Kozlowski et al., 1996). The circumstances surrounding app use (e.g., at home, alone, with alcohol, etc.) will be assessed.

Feedback and App Usage. The System Usability Scale (SUS) measures participants' perception of usability and learnability (Brooke et al., 1996; Lewis & Sauro, 2009). We will develop a questionnaire with Likert scale items to capture the following areas: reality/co-existence of the AR images (e.g., How realistic did the AR images appear?), usefulness (e.g., How useful was this app for smoking craving this past week?), ease of use (e.g., How easy/difficult did you find using the app?); ease of learning (e.g., How many days did it take to get comfortable using the app?); and satisfaction (e.g., Would you recommend this app to a friend or family member to help them quit smoking?). Overall, how satisfied were you with the app?). During the phone interview, participants will be asked open-ended questions on their perceptions of the app. Interviews will be tailored to participants' app use to understand challenges and barriers among those with low app use (completed <5 AR sessions) and to receive feedback from those with high app use (completed 5 or more AR session). Examples of questions include: "What changes would you make to the app to increase the likelihood of using it, or, to make it more enjoyable?; What was the easiest part of using the app?; What was most difficult?; What was most interesting? (see appendices). We will also have access to the real-time app use metadata, including proportion of sessions started, completed, etc.; number of unfinished sessions; time spent in the app; days of use; engagement with app features (e.g., tracking, rewards). We will query during the phone interview why any app feature was not used.

AIM 2 Measures

Measures assessed via the app were described for Aim 1. Additional measures unique to Aims 2 and 3 are described below. REDCap will be programmed to email and text participants a survey link to complete measures at baseline, around 5 weeks post initial app engagement, and around 6 months post-baseline.

Questionnaires. Demographics and Smoking History will collect data on variables including gender, age, race, marital status, income, education, and smoking history (e.g., number of quit attempts, years smoked). Heaviness of Smoking Indiex (HSI; Heatherton et al., 1989) is a widely used measure of nicotine dependence. We will also administer the subscales of Automaticity and Affective Engagement of the Brief Wisconsin Inventory of Smoking Dependence Motives (WISDM-38), a multidimensional assessment of motivational factors associated with smoking behavior (Smith et al., 2010). We are particularly interested in the Cue-Exposure/Associative Processes scale, which assesses the degree to which smoking is driven by cue reactivity. Therefore, we will include the full subscale from the original WISDM-68 (Piper et al., 2004), due to its superior psychometrics (Smith et al., 2010). We will use the Self-efficacy Scale – Smoking to assess level of confidence for not smoking in various situations (Velicer et al., 1990). Positive and Negative Affect Schedule short form (PANAS; Thomson, 2007) will assess affect. Aside from their descriptive value, these measures will allow for testing moderators of the study outcomes. These measures will be administered at each assessment.

App Use, Evaluation, and Extinction. Similar to Aim 1, we will collect metadata on app use as an

indicator of treatment engagement. Primary treatment engagement variables of interest that are linked to our theoretical model of extinction and that are related to increased abstinence include: greater completion of the AR sessions (e.g., multiple times per day over several days), conducting the AR sessions in several different locations (to increase generalizability of extinction), and less use of avoidance strategies during the AR sessions (e.g., using distraction or other behaviors to avoid experiencing craving). Avoidance strategies will be assessed at the 5 week survey via a checklist of avoidance strategies and the frequency that they occurred during AR sessions. We will also collect self-reported treatment satisfaction using a modified version of the Client Satisfaction Questionnaire (Attkisson & Greenfield, 1994), the SUS (Brooke et al., 1996; Lewis & Sauro, 2009), and unique items to assess features and functions of the app and the AR experience, including the App coach. Extinction magnitude (degree of craving reduction over time) and latency (time to meeting extinction criteria) will also be derived. For participants who never achieved abstinence during the 5 weeks of app use, thus, never completed AR sessions, versions of the follow-up surveys will omit items specifically related to AR use. For participants who achieved abstinence, but did not complete more than 4 AR sessions, there will be questions at the 5-week survey regarding barriers to completing the AR sessions.

Quitline Usage and App Coaching. Basic information on participant interactions will be provided to the study team from the quitline, including call completion dates, quit status (planned and actual quit dates), and NRT that was shipped. For those in QL+AR, we will track calls completed with an App coach.

Tobacco Abstinence. The primary outcome measure will be 7-day point prevalence abstinence (defined as self-report of no combustible tobacco use in the past 7 days; Piper et al., 2020) around 6 months post-baseline. Reported abstinence will be confirmed in approximately 40% of self-reported abstinent participants using a saliva cotinine level cut-off of <10 ng/ml (Benowitz et al., 2020). Cotinine analysis using ELISA assay will be conducted by Salimetrics (Carlsbad, CA).

Cost-assessment and Cost-effectiveness. An important step in evaluating feasibility of interventions is showing that the intervention can be performed at a (relatively) low cost while improving outcomes. We will assess the resource utilization associated with both arms of the intervention, allowing us to determine the relative costs and cost-effectiveness of the arms. Our cost-assessment methodology will be done initially from the perspective of the health care system and based on collecting information on all resources used in the intervention and affixing a standardized “price” to those resources. This approach, long recommended as the most appropriate means of calculating true resource costs (Sanders et al., 2016; Dranove, 1996; Weinstein et al., 1996), results in “costs” that are comparable both among participants within an intervention and between interventions. We have successfully used this methodology in previous studies (e.g., Byrne et al., 2006; 2014; Martinez et al., in press; Medina-Ramirez et al., 2019; 2020; Morgan et al., 2008).

Quality of Life. To assess potential improvements in quality of life, we will assess smoking-related health items from the Tobacco Quality Of Life Impact Tool™ (TQOLIT v.1; Ware JE; Gandek B; Kulasekaran A; Guyer R, 2015) which includes 8 items that measure the frequency of smoking-related symptoms (e.g., bad breath, difficulty breathing). We will also use the EQ-5D-5L which consists of the EQ-5D descriptive system that measures health using five levels of severity in five dimensions (mobility, self-care, usual activities, pain/discomfort, anxiety/depression) and the EQ visual analogue scale (EQ VAS) that records the individual's self-rated health on a vertical visual analogue scale, where the endpoints are labelled 'The best health you can imagine' and 'the worst health you can imagine (Herdman, et al. 2011). Each of these measures will be included in the Baseline and 6 Month surveys.

Implementation Barriers and Facilitators. To identify barriers and facilitators of incorporating AR treatment into the quitline, interviews will be conducted with a subset of quitline supervisors, all App coaches, and a subset of participants. The interview guide will be structured around the Consolidated Framework for Implementation Research and assess multi-level barriers and facilitators for implementation. For example, the guide will assess information about *intervention characteristics* (e.g., technical challenges with AR app), *organizational characteristics* (e.g., compatibility of the app with quitline workflow), individual characteristics (e.g., beliefs about the AR app, self-efficacy for app use), *process* (e.g., sufficiency of training and engagement strategy), and *external context* (e.g., how well the app fits with quitline external incentives and policies). A brief survey will capture demographic information.

Questions will be asked to quitline supervisors (e.g., What training is needed to train quitline coaches to train callers in using the AR app?; What concerns do you have about quitline callers using the app?) and App coaches (e.g., What additional training would be useful as an App coach?; What were some common issues participants reported having and do you have any thoughts on how to resolve those more effectively?; What challenges did you encounter as a coach?). A small subset of 20 participants who used the AR app feature (AR use = 10+ times) will be randomly selected and asked about their experiences (e.g., What features of the AR app could be improved?; What challenges did you encounter with the app?; How might we improve the App coaching you received?). To learn how to improve engagement, we will also contact 10 participants who failed to engage with the AR app feature (AR use = 0 times), and 10 who engaged but prematurely discontinued using the AR app feature (AR use = 1-4 times). Thus, a total of 40 participants will be included.

Data Safety and Monitoring Plan

The data and safety monitoring plan development for this project is commensurate with the expected minimal risks posed by the project. Data and safety monitoring will be ongoing by the Principal Investigators, Moffitt Cancer Center's Protocol Review and Monitoring Committee, the Data and Safety Monitoring Board (DSMB), and the Institutional Review Board (IRB). Overall, the plan for monitoring includes: 1) Monitoring the progress of the studies and safety of participants; 2) Assuring compliance with the requirements for reporting adverse events that may occur during the study; 3) Assuring any action resulting in a temporary or permanent suspension of a study is reported to the NIH official who is responsible for the grant; and 4) assuring data accuracy and protocol compliance. Participant data will be associated with participant study ID and not directly associateable with names or other identifying information. Questionnaire/interview data will be collected and recorded via computer and will only be identified with the participant's study ID. The PIs will keep the codes that link the name of the participant and the study ID confidential in a password protected electronic file. Data accuracy will be subject to random audit. Monthly data management reports will be made by the project manager (with oversight by the study statistician), including data entry progress, error rates, range checks, and general descriptive statistics. The investigators and research staff will conduct all data analyses using primarily SPSS and SAS software. Participants who elect to be informed of study findings will be sent summaries of the research findings upon the completion of data analysis.

Research staff will report any potential AEs immediately to the PIs. Any SAEs will be reported within two days to the IRB and NIH using the required reporting format. We will use the FDA definitions of AE (any untoward medical occurrence associated with the [intervention] in humans, whether or not considered [intervention] related) and SAE (an AE that results in any of the following outcomes: death, a life-threatening adverse event, inpatient hospitalization or prolongation of existing hospitalization, a persistent or significant incapacity or substantial disruption of the ability to conduct normal life functions, or a congenital anomaly/birth defect). Given the very low-risk nature of our behavioral intervention, the likelihood of suspected SAEs is extremely low. Any IRB actions in relation to this protocol will also be reported to NIH.

As noted above, this project will have a DSMB comprised of individuals with expertise in the necessary content areas (e.g., mHealth, tobacco, statistics). We have already identified three individuals with expertise in these areas who have agreed to serve on the DSMB, assuming we receive funding – [name]. (University of Pittsburgh; tobacco use and cue exposure), [name]. (University of Oklahoma; smoking cessation interventions and mHealth), and [name]. (University of South Florida; statistician with expertise in longitudinal data analysis). The primary role of the DSMB will be to evaluate the safety and efficacy of the study as it is ongoing, and to provide recommendations as needed on the protocol. Data on participant progress through the study (e.g., recruitment, retention), protocol compliance, and any protocol deviations and AEs/SAEs will be monitored. DSMB meetings will occur twice per year, with a report provided to the committee in advance of the meeting for review. A final report will be drafted following the meeting and will

be forwarded to the necessary stakeholders (e.g., NIDA, IRB). Additional meetings, phone calls, and emails will be exchanged between meetings as needed.

Drs. [name] and [name] will implement standardized procedures for each Aim. This will include weekly meetings to discuss any issues related to the progression of the project and factors that may affect the outcome, including a review of data quality and security, recruitment, and retention. For any problems that may arise, including adverse events, a discussion among the investigators will be conducted.

